9.21. Three month Quality of Life postal questionnaire

After three months we will send parents (or email, depending on their preferred mode of communication) a Quality of Life Questionnaire which will contain the CHU-9D and the OMQ-14 validated questionnaires. Parents receiving the postal version will also be sent prepaid return addressed packaging for the return of the paper questionnaire to the study team.

In order to keep parents informed of the forthcoming questionnaire, we will telephone or email them (depending on their preferred mode of communication), sending a short, standard message two weeks before the postal or online questionnaire is sent out to let the parent know that they will be receiving it on or around a specific date.

10. DATA COLLECTION

10.1. Justification for quantitative data collection instruments

Antibiotic consumption

Since our work has shown that any (vs. no) antibiotic use is known to influence antimicrobial resistance,¹⁰ we will record the use of any antibiotics by mouth in the 7 days following randomization (where Day 1 is the day of randomization, and Day 8 is the seventh day after the day of randomisation). We will also record the number of doses of antibiotics given in the first 7 days post randomisation (Symptom and Recovery Questionnaire), the type of antibiotic prescribed (baseline Case Report Form and primary care notes review), and the dose and number of days for which the antibiotic was prescribed (primary care notes review).

Child ear pain

We have used the PeDIMMPACT (Paediatric Initiative on Methods, Measurement, and Pain Assessment in Clinical Trials) recommendations¹³ in selecting the zero to ten pain numerical rating scale (used in our previous trial⁶) for our primary outcome. Although no parent completed pain score for younger children can completely overcome the challenge of differing parental and child pain perceptions, this scale has been shown to be valid and sensitive to change across the full trial age group, provide a global measure of pain for a 24 hour period (which is reflected

in the eligibility criteria and therefore does not restrict recruitment to pain scores within specified time periods), and in combination with our other outcomes, meet the PeDIMMPACT recommendations.

Figure 8.1.1: the 0-10 Numeric Pain Rating Scale

To complement this, and in order to measure any potential difference in parent and child pain perception, we will ask children aged \geq 5 years to record pain using the Faces Pain Scale – Revised (FPS-R) which also rates pain zero to ten.¹⁴

Figure 8.1.2: the Faces Pain Scale – Revised (FPS-R) [Hicks et al 2001]

The Faces Pain Scale – Revised (FPS-R) was selected as the trial's self-report measure of pain intensity for children who are old enough to score their own pain (5 years and above), as the problem of confounding the faces at either end of the scale with emotional states was less likely than with the Wong-Baker FACES pain scale [Stinson et al 2006] which is extensively used in clinical practice.

We are aware that the majority of the children recruited to CEDAR will be too young to be able to self-report their ear pain, and that the FPS-R is not validated for use in such children, for whom behavioural observational scales are recommended (e.g. the FLACC scale [Merkel et al 1997]). A behavioural observational score, however, cannot be considered to be equivalent to a 0-10 parent-rated pain score or a 0-10 FPS-R self-score (for children aged 5 or above). Furthermore, the behavioural observational score could only be completed by the parent, from whom we are already requesting their perceived child ear pain rating on the 0-10 numeric scale.

We will collect both parent and child pain scores where possible, at presentation, after presentation (as close as possible to 60 minutes after giving the first dose of the ear drops, a time point informed by feedback obtained from our PPI representatives) and on the evening of Day 1, and all following evenings "at the end of the day" (recording the time they do so also). Pain is mostly worse in the evening/night therefore collecting this data in the evening when the symptom is likely to be peaking is sensible.

We will ask parents (and children) to record pain bearing in mind that the parent score, as stipulated in the diary, will reflect pain over the previous 24 hours, but the child score will reflect the pain now. To fully interpret the latter, we will therefore also need to record the timing of drops, paracetamol, ibuprofen and other pain-relieving therapies.

Other symptoms

Other symptoms will be measured using a validated⁵¹ Symptom and Recovery Questionnaire, as per our other paediatric studies.^{6 52}

Preference based quality of life

There is currently no single valid preference based measure of utility (for calculating QALYs), that can be used in children from age 12 months to 10 years. Most generic measures (e.g. HUI3, EQ-5D Y, CHU-9D) are not designed for or validated in pre-school (i.e. the majority of children in CEDAR). The CHU-9D data, for example, is a preference-based instrument that can be used for QALY calculation in school aged children (7-10 years).

Therefore, we propose a dual approach: parents of all children aged 2 and older will be asked to complete the disease specific OMQ-14¹⁹ at baseline and 3 months, for ear problem related quality of life. The OMQ-14¹⁹ is a subset (14 of 30 items from the OMQ30) and has been successfully used in previous⁵³ and the current HTA funded 'AIRs trial' (PI [name] for both trials). Parents of school aged children (\geq 5 years) will also be asked to complete the generic CHU-9D¹⁸ preference measure at baseline, 24 hours, 7 days and 3 months after randomisation. As a preliminary secondary analysis, which would allow some comparison with other interventions, the CHU-9D data and multiple imputation will be used to calculate QALYs for those children outside the 7-10 year age range.

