- Baseline sociodemographic factors: parental occupation, child's ethnicity, maternal smoking habits, number of other children in the child's home, and whether the child was breastfed at 3 months (the rationale for collecting these data at this point is also to reduce the pressure on recruitment within the GP consultation);
- The child's daily parent-rated ear pain score (average over the preceding 24 hours);
- Children aged five years and above will be asked to rate their own ear pain;
- Presence of any ear discharge (if yes, parent will be advised to stop using ear drops immediately);
- Number of doses of ear drops administered, and to which ears;
- Whether the child has taken any antibiotics by mouth today;
- Number of doses of rescue analgesia administered;
- Parent's rating (mild, moderate or severe) of the child's other symptoms over the preceding 24 hours, including: episodes of distress or crying; disturbed sleep; interference with normal activities of daily living; eating or drinking less than normal; fever; hearing problems; any other symptoms (potential adverse events);
- Has the child missed any school, nursery or childcare today
- Has the parent or carer lost time from work today

On the Day 1 telephone call, the Research Nurse will remind the parent to complete the CHU-9D quality of life questionnaire for their child on the following day, at 24-36 hours post recruitment – i.e. on Day 2.

Days 2-7: parents will receive another two calls, at their convenience, to support them in completing the first week of the daily Symptom and Recovery Questionnaire. The calls will guide the parent through the daily Symptom and Recovery Questionnaire and transcribe the data collected over the phone onto the 'office use' shadow Symptom and Recovery Questionnaire at the trial centre. The information for which the Nurse will ask the parent for each day is as follows:

- Day 2 only: Child's quality of life over the previous 24 hours using the CHU-9D validated questionnaire;
- The child's daily parent-rated ear pain score (average over the preceding 24 hours);
- Children aged five years and above will be asked to rate their own ear pain;
- Presence of any ear discharge (if yes, parent will be advised to stop using ear drops immediately);
- Number of doses of ear drops administered (up to a maximum number of 8 days), and to which ears;
- Whether the child has consumed any antibiotics by mouth today;
- Number of doses of rescue analgesia administered;

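### The evening child score (pain now) and the parent score (24-hour average) cannot measure parent-child difference in pain perception, because rater and recall window are confounded

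*Protocol*

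**What the plan says.** Section 10.1 (Child ear pain) gives the parent 0-10 numerical rating scale as the main pain measure. It adds the FPS-R, also scored 0-10, for children aged 5 and over. The reasons given are to complement the parent score and "in order to measure any potential difference in parent and child pain perception".

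The section then sets the recall windows. For the parent, "the parent score, as stipulated in the diary, will reflect pain over the previous 24 hours". Section 9.17 describes this score as an "average over the preceding 24 hours", and sections 4.3 and 9.11 agree. For the child the sentence continues "but the child score will reflect the pain now".

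Both scores are taken "on the evening of Day 1, and all following evenings", with further ratings at presentation and about an hour after the first dose. The reason for the evening is that "Pain is mostly worse in the evening/night". The clock time of each rating is recorded. To interpret the child score, the section adds that "we will therefore also need to record the timing of drops, paracetamol, ibuprofen and other pain-relieving therapies".

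**The concern.** A difference in perception is a difference between two people rating the same thing. Here the parent summarises a day and the child reports a moment, and the moment is one at which the protocol itself expects pain to be away from its daily average. A gap between the scores could come from the raters, from the windows, or from both. No gap could mean agreement, or two effects that cancel.

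What is at stake is limited to this one stated use of the FPS-R. A report that parents under-rate or over-rate their child's pain could be an artefact of timing, and so could a report that they agree.

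**Working it through.** The protocol states no figure for the parent-child difference, so there is none to reproduce. The check is structural, followed by an illustration on stated assumptions.

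**Structure.** Let p(t) be the child's true pain and T the time of the evening rating. Then

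child score − parent score = (rater difference) + (scale difference, FPS-R against numerical scale) + [p(T) − mean of p over the 24 hours before T].

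The term in square brackets is the window effect. To separate it from the rater difference, one rater would have to supply both windows, or both raters the same window. The diary items in sections 9.11 and 9.17 include neither a parent momentary rating nor a child 24-hour rating. For the ratings at presentation and at about 60 minutes, no different parent window is stated, so they offer no evident matched pair.

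Dose and rating times show what preceded T. They do not give the pain level during the rest of the day, which is what the bracket needs. Two successive evening child scores give the two ends of the 24-hour window, so they could show a trend. They say nothing of the day and night between.

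**Illustration.** Assume identical perception and interchangeable scales, so that only the bracket remains. Take

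p(h) = M · exp(−k(h − 7)) · [1 + A · cos(2π(h − 22)/24)],

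with the child rating at 19:00 and the parent score equal to the mean over the previous 24 hours.

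- M, the underlying level at the middle of the window, is 5.5 to 6.5. These are the mean scores at 24 hours that section 12.1 cites from the investigators' previous trial.
- A, the relative size of the evening peak, is 0 to 0.4 (assumed).
- k = ln 2 / (24 × half-life in days), with a half-life of 3 days, 1 day, or no decline (assumed).
- The 22:00 peak and the 19:00 rating are also assumed.

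*Steady pain with an evening peak.* Difference = M · A · cos(2π · 3/24) = 0.707 · M · A.
- A = 0.1: 0.707 × 5.5 × 0.1 = +0.39, and with M = 6.5, +0.46.
- A = 0.4: 0.707 × 5.5 × 0.4 = +1.56, and with M = 6.5, +1.84.

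*Falling pain without a daily pattern.* Difference = M · [exp(−12k) − sinh(12k)/(12k)].
- 3-day half-life: 12k = 0.1155, bracket = 0.8909 − 1.0022 = −0.1113, so −0.61 to −0.72.
- 1-day half-life: 12k = 0.3466, bracket = 0.7071 − 1.0201 = −0.3130, so −1.72 to −2.03.

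*Both together, 3-day half-life (evaluated numerically).*

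| A | M = 5.5 | M = 6.5 |
|---|---|---|
| 0.1 | −0.28 | −0.33 |
| 0.2 | +0.05 | +0.06 |
| 0.4 | +0.71 | +0.84 |

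The sign and size of the artefact depend wholly on a within-day pain curve that the documents do not give. With matched windows the bracket is zero by construction.

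**The case against.** The strongest reply is that the mismatch is disclosed. Section 10.1 states the two windows in one sentence, has families record the time of each rating, and asks for the timing of drops and analgesics so that the child score can be interpreted. That is true, but disclosure does not align the windows, and those records do not supply the missing rating.

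A second reply is that the comparison carries little weight. It is not among the research questions in sections 5.3 and 5.4, has no row in Appendix 7 and has no analysis in section 12.5. The FPS-R is also a secondary outcome in its own right in section 11. Comparing it between arms is sound, because every child rates the present moment. This stands, and it is why the point is minor. Leaving the agreement analysis to a statistical analysis plan would not help, because the gap is in what is collected.

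Three stronger readings are tempting, and the documents do not support them.

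- A reader might infer that the scores will differ even when parent and child perceive the same pain. The evening peak and falling pain pull in opposite directions and can cancel, as the A = 0.2 row shows.
- A reader might infer that the key secondary outcome is undermined. That analysis compares parent scores with parent scores over the same window, and sections 7.4 and 12.3 keep parents in the three-arm trial blind to active or placebo drops. Section 10.1 rests its trust in the parent scale on stated validity and sensitivity to change, not on the FPS-R comparison.
- A reader might set the artefact against the 1-point difference in section 12.1. That figure is for active against placebo drops and is no yardstick for parent-child agreement.

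**Conclusion.** The point holds as a minor defect: section 10.1 states a purpose that the data it specifies cannot serve. In the evening pairs rater and recall window are completely confounded, so neither a difference nor its absence can be read as evidence about perception. This follows from the protocol's text and needs no numerical assumption.

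The size and direction of the artefact are unknown. The range of about −2.0 to +1.8 points is illustrative only. It rests on an assumed daily pattern, assumed rates of decline, and pain levels borrowed from a previous trial. The primary and key secondary between-arm comparisons are not affected.

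**What to change.** For children aged 5 and over, add a parent 0-10 rating of the child's pain now, at the time of the child's evening score. It should be recorded before that score and independently of it, so that the child's answer does not influence the parent's. Base the parent-child comparison on that pair only. State in section 10.1 that the remaining difference still includes the difference between the numerical scale and the FPS-R, because matching the window does not match the instrument. Leave the 24-hour parent score for the key secondary outcome unchanged.

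The cost is one extra diary item per evening for parents of children aged 5 and over, in a diary whose burden was discussed with the patient and public involvement group, plus a sentence of analysis text. If that burden is not accepted, the alternative adds no data collection: delete the stated purpose of measuring parent-child difference, and present the FPS-R only as a self-report outcome compared between arms.

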10.2. Summary of quantitative trial data collection

Day 1 (baseline data collection collected by Responsible Clinician at the index consultation) will include: eligibility criteria; age; gender; postcode; parent telephone number; summary of symptoms (including pain score); clinical examination findings; significant co-morbidities; clinician diagnosis; CHU-9D and OMQ-14. The Trial Nurse will try to make contact on Day 1 to address any questions or concerns about the trial. The Patient Pack will contain a £5 voucher to thank parents for helping with baseline data collection.

Days 1 to 8 (Symptom and Recovery Questionnaire supported by Trial Nurse telephone call) will include daily: global measure of pain numerical rating score (*key secondary outcome at 24-36 hours*); symptom burden; CHU-9D (Day 1 and Day 2); adverse events; antibiotic doses, ear drop and other analgesic use. As per previous studies,⁵² parents will be asked to record these until two days of symptom resolution, which for AOM is thought be eight days (for 90% of children).¹⁷

Day 8 (Symptom and Recovery Questionnaire supported by Trial Nurse/Administrator telephone call) will include antibiotic consumption (*primary outcome*) and daily: pain scores; symptom burden; adverse events; ear drop and other analgesic use; CHU-9D; NHS contacts; days off school/nursery; carer lost productivity and other expenses. The Trial Nurse/Administrator will also ask parents, at the Day 8 telephone call, about: carer opinion of, and satisfaction with, treatment allocation, intention to purchase drops if available OTC, their beliefs about the likely benefits of antibiotics, and ask the parent to return: (i) the ear drop bottle with any unused drops, and (ii) any used antibiotic packaging with unused antibiotics, in pre-paid, pre-addressed protective envelopes. The ear drop bottles will be weighed on receipt as a measure of trial medication adherence. The study team will send the parent a £5 voucher on completion of the Symptom and Recovery Questionnaire.

Post Day 8 (Trial Nurse/Administrator telephone call): Parents whose children are still experiencing ear pain at after 7 days following the day of randomisation will continue to be telephoned twice weekly in order to identify the date on which the child's parent-reported ear pain had resolved for two consecutive days, without analgesic medication. We estimate that 10% of children will still be symptomatic at this point (Day 8)¹⁷. Parents will be asked to score their child's ear pain (on average over the preceding 24 hours) and to report any oral antibiotic or analgesic consumption.

Month 3 (primary care notes review and postal/ telephone questionnaire) will include: primary care notes review for primary and secondary care attendances, and Serious Adverse Events and a postal/telephone questionnaire to collect CHU-9D and OMQ-14, following which the study team will send the parent a £5 voucher.

10.3. Observational study data collection

Data collection for the observational study will be exactly the same as for the trial, with the exception of questions about use of ear drops.

10.4. Qualitative data

All interviews will be conducted by telephone. At interview, participants will be asked to give verbal consent, following which a flexible topic guide will be used to ensure primary issues are covered during all interviews, but without dictating data collection, allowing participants to introduce unanticipated issues. Topic guides will be modified as necessary to reflect emerging findings. The researcher will use open-ended questioning techniques to elicit participants' experiences and views of key events and participants will be asked to provide examples. Interviews with health care professionals are expected to last around 30 minutes and interviews with parents' around 45 minutes, and will be recorded using a digital voice recorder, transcribed and anonymised to protect confidentiality. Parents who take part in interviews will receive a £10 High Street voucher.

As well as parents participating in the RCT, we will also endeavour to conduct qualitative telephone interviews with parents who have declined RCT participation, and with parents who have chosen to withdraw (n=10).

11. ASSESSMENT OF EFFECTIVENESS

Primary outcome

1. Any antibiotic consumed by Day 8 (measured using daily Symptom and Recovery Questionnaire with telephone support calls during week 1), where Day 1 is the day of randomisation;

Secondary outcomes

[Key secondary outcome]

2. Ear pain over first 24-36 hours post randomisation using the parent completed, validated numerical rating scale successfully used in our previous trial⁶ (Symptom and Recovery Questionnaire with telephone support call in first three days).

[Other secondary outcomes]

- 3. Time taken before antibiotics started (Symptom and Recovery Questionnaire with telephone support calls during week 1);
- Daily symptom severity (until illness resolution i.e. child free of ear pain without need for rescue analgesia for two consecutive days, expected by 8 days for most children¹⁷) including episodes of distress/crying, disturbed sleep, interference with normal activity, appetite, fever and hearing problems (Symptom and Recovery Questionnaire, supported by telephone calls);
- 5. Child completed Faces Pain Scale-Revised (FPS-R [Hicks et al 2001], for children aged ≥5 years) (Symptom and Recovery Questionnaire);
- 6. Adverse events (Symptom and Recovery Questionnaire, supported by telephone calls);
- 7. Ear drop and rescue analgesia consumption (Symptom and Recovery Questionnaire, supported by telephone calls);
- Parent satisfaction with, and opinion of, treatment allocation and future intention to use drops (with/without prior GP consultation if drops were to become available over-the-counter) after 7 days (Symptom and Recovery Questionnaire, with telephone support call at one week);
- Preference based quality of child life measured (baseline, 24-36 hours, 7 days and 3 months post randomisation) using CHU-9D¹⁸ for children age ≥5 years (CRF, Symptom and Recovery Questionnaire supported by telephone calls, and postal/online questionnaire at 3 months)
- 10. NHS costs up to 7 days after randomisation (Symptom and Recovery Questionnaire, supported by telephone call at one week) and contacts to 3 months (primary care medical notes review);

- 11. Child's school/nursery absences, parent lost productivity and other expenses up to 7 days after randomisation (Symptom and Recovery Questionnaire, supported by telephone calls)
- 12. Child's quality of life (OMQ-14,¹⁹ for children aged 2 years and older) at baseline and 3 months after randomisation (CRF and postal/online questionnaire at 3 months).
- 13. Qualitative outcomes to assess acceptability, barriers and adherence, a purposeful sample of parents and clinicians will be asked to participate in qualitative interviews to explore experiences of, and attitudes to AOM and its treatment.

12. ANALYSIS

12.1. Sample size calculation

Antibiotic consumption (primary outcome)

Current United Kingdom (UK) antibiotic prescribing rates are high for children with AOM, in fact higher than for any other respiratory infection of childhood.⁸ One study showed prescribing rates of 84%,⁹ while another showed three-quarters of UK general practices prescribe antibiotics to at least 80% of children with AOM.⁸ We are not aware of any evidence to inform consumption rate, but our clinical experience and PPI group suggest that the majority of parents will give their child a prescribed antibiotic. Our power calculation therefore (conservatively) assumes a no drop (usual care) arm antibiotic consumption rate of 80 to 90%. While it is agreed that for reducing the development of antimicrobial resistance, antibiotic consumption is more meaningful than prescribing, there is no agreed minimum difference in antibiotic consumption worth detecting. Our work has shown a clear and prolonged link between primary care prescribed antibiotics and antimicrobial resistance lasting over 6 months,¹⁰ and although we did not find evidence to define a clinically important difference in consumption rates, these data¹⁰ suggest that a 20% change in consumption could have important effects on antimicrobial resistance, both in children and in their infectious contacts. Assuming a Type II error rate of 0.1 (90% power) and Type I error rate of 0.05 (alpha) the number of children needed in each group (active eardrops and no drops) ranges from 92 to 119 to demonstrate a 20% fall in antibiotic consumption from 80-90% in the control group to 60-70%. Using the more conservative estimate of 119, and taking into account 20% attrition, this would give a final sample size of 149 per arm.

Pain (secondary outcome)

The pain the child suffers is an important outcome for parents and will be a key secondary outcome, comparing whether the active drops are more effective than placebo drops. We will measure pain using the validated zero to 10 numerical rating scale we used in our previous RCT of delayed vs. same day antibiotic for childhood AOM.⁶ This trial showed mean pain scores of around 6.5 (same day antibiotics) and 5.5 (delayed) at 24 hours and overall mean pain scores of 2.6 (same day) and 3.6 (delayed). Regarding the minimum clinically important difference, our PPI group indicated that they would find a 10% (or greater) reduction in pain useful, and the largest difference observed in our previous trial using the same Symptom and Recovery Questionnaire was one point [[name] BMJ 2001]. Again assuming 90% power and α =0.05 we can detect a mean difference of 1 (SD=2.5 based on trial data) in pain score between the active and placebo ear drop groups, with 133 children per arm. Assuming 20% attrition and equal numbers in the three groups, we need 167 children per arm of the trial (more than for the primary outcome) and therefore 501 children in total.

